3.0 Trial Design

This is a prospective, single arm, seamless phase I/II cohort study (investigator initiated trial) with a planned total accrual of 28 patients.

4.0 Study Population:

Potentially eligible patients are adults with surgically inoperable, biopsy proven or suspected single T1N0 or T2N0 Non-small cell lung cancer tumor or patients with a single pulmonary metastasis (<4 cm maximal tumor dimension) from a known primary malignancy of any histology (either metastatic failure to a single pulmonary site after primary radical treatment, or metastatic progression to a single lung metastasis following palliative chemotherapy with no other sites of uncontrolled disease). Tumors should be located either in the lower lobe, lingula, or right middle lobe of the lung however, patients with upper lobe tumors are eligible as long as the tumors have a respiratory amplitude of ≥ 1 cm. Tumors should be located at least 2 cm from the proximal bronchial tree (non-central tumors).

5.0 Eligibility Criteria:

- 1) Adult ≥ 18 years of age who is surgically inoperable, or refusing surgical management.
- 2) Tumor criteria (a patient must satisfy one of “a”, “b” below to be eligible):
 - a. AJCC 7th edition clinical T1aN0M0, T1bN0M0, or T2aN0M0 (<4cm) Non-small cell lung cancer (adenocarcinoma, squamous cell carcinoma, or NSCLC Not Otherwise Specified) of the middle or lower lobes of the lung*;
 - b. A single pulmonary metastasis (<4cm) of a known primary malignancy of any histology involving the middle or lower lobes of the lung* (either metastatic failure to a single pulmonary site after primary radical treatment, metastatic progression to a single lung

[figure not shown]
metastasis following palliative chemotherapy, or a single pulmonary metastatic lesion of newly diagnosed stage IV malignancy).

*upper lobe tumors are eligible for trial participation if the tumor has a demonstrated tumor motion of ≥ 1 cm in any axis (as assessed by fluoroscopy at the time of bronchoscopy).

- 3) Confirmation of malignancy (a patient must satisfy one of “a”, “b” below to be eligible):
 - a. Tumors accessible by bronchoscopy, image-guided percutaneous biopsy, or other invasive staging methods require biopsy confirmation of malignancy.
 - b. If a tumor is not amenable to a diagnostic biopsy, evidence of growth of the target tumor on serial imaging scans is necessary prior to enrollment. An increase in SUV of the target tumor on serial PET scans is also acceptable.

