- 4) ECOG performance status of 0 to 2.
- 5) Minimum life expectancy of 6 months.
- 6) Deemed fit to undergo bronchoscopy by their participating thoracic surgeon
- 7) Deemed fit to undergo SABR by their participating Radiation Oncologist.
- 8) Respiratory function (a patient must satisfy both “a” and “b” below):
 - a. Minimum FEV1 of 0.8 liters
 - b. Minimum DLCO of 35% predicted.
- 9) Able to provide written informed consent and understand verbal instructions necessary for radiotherapy treatments.

Exclusion Criteria:

- 1) Tumors located < 1 cm from the chest wall based on CT imaging.
- 2) Tumors located ≤ 2 cm from the proximal bronchial tree (see figure 7)
- 3) Patients who require supplemental oxygen at rest.
- 4) Patients who are unable to lie flat or still for a minimum of 30 minutes.
- 5) ECOG performance status 3 or 4.
- 6) Evidence of uncontrolled extra-thoracic metastatic disease (based on imaging or clinical findings).
- 7) Proven or suspected intrathoracic lymph node involvement.
- 8) Prior SABR to the target tumor.
- 9) Prior history of idiopathic pulmonary fibrosis, interstitial lung disease, or active collagen vascular disease (systemic lupus erythematosus, Rheumatoid arthritis, or Scleroderma)
- 10) Pregnancy.
- 11) Active pulmonary infection
- 12) Known hypersensitivity to nickel titanium (Nitinol)
- 13) Known Bronchiectasis of the small airways nearest to the tumor

Figure 7: The proximal bronchial tree (tumours within this region are ineligible for trial participation).**6.0 Study Objectives:****Phase I:**

- 1) To allow for members of the interdisciplinary care team (Thoracic surgeons, Radiation Oncology, Radiation Therapists, and Medical Physicists) to familiarize themselves with the clinical use of implanted endobronchial tumor tracking beacons and carry out quality assurance assessments in preparation for the subsequent phase II component of the study.
- 2) To quantify the presence (if any) of beacon migration (inter-beacon distance) at different time points in a patient's care path (time of implantation, CT simulation scan, and days of SABR treatment).
- 3) To assess the quality of life of patients having Calypso placement (EORTC QLQ - LC13 questionnaire)
- 4) To assess acute toxicity of beacon implantation using the Common Terminology for Criteria for Adverse Events (CTCAE version 4.0)

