| | none | minor | none | minor | none | minor | none | minor | |
| 2.0 | <1.2 | 1.2-1.4 | <3.9 | 3.9-4.1 | <28.1 | 28.1-30.1 | <10 | 0-15 | 1.8 |
| 2.5 | <1.2 | 1.2-1.4 | <3.9 | 3.9-4.1 | <28.1 | 28.1-30.1 | <10 | 10-15 | 3.8 |
| 3.0 | <1.2 | 1.2-1.4 | <3.9 | 3.9-4.1 | <28.1 | 28.1-30.1 | <10 | 10-15 | 7.4 |
| 3.5 | <1.2 | 1.2-1.4 | <3.9 | 3.9-4.1 | <28.1 | 28.1-30.1 | <10 | 10-15 | 13.2 |
| 4.0 | <1.2 | 1.2-1.4 | <3.8 | 3.8-4.0 | <30.4 | 30.4-32.4 | <10 | 10-15 | 21.9 |
| 4.5 | <1.2 | 1.2-1.4 | <3.7 | 3.7-3.9 | <32.7 | 32.7-34.7 | <10 | 10-15 | 33.8 |
| 5.0 | <1.2 | 1.2-1.4 | <3.6 | 3.6-3.8 | <35.1 | 35.1-37.1 | <10 | 10-15 | 49.6 |
| 5.5 | <1.2 | 1.2-1.4 | <3.5 | 3.5-3.7 | <37.4 | 37.4-41.7 | <10 | 10-15 | 69.9 |
| 6.0 | <1.2 | 1.2-1.4 | <3.3 | 3.3-3.5 | <39.7 | 39.7-41.7 | <10 | 10-15 | 95.1 |
| 6.5 | <1.2 | 1.2-1.4 | <3.1 | 3.1-3.3 | <42.0 | 42.0-44.0 | <10 | 10-15 | 125.8 |
| 7.0 | <1.2 | 1.2-1.4 | <2.9 | 2.9-3.1 | <44.3 | 44.3-46.3 | <10 | 10-15 | 162.6 |

11.0 Potential Adverse Reactions:

The adverse effects associated with the use of the Calypso transponder beacons are similar in profile to other bronchoscopic procedures such as bronchoscopic biopsies or the implantation of inert gold seed fiducial markers.

Pneumothorax: The most commonly encountered adverse effect of fiducial marker placement is pneumothorax which has a risk of between 2 to 5 percent^{27,28} with the majority of these treated either conservatively or with a pigtail catheter for a day or two²⁴ after the procedure.

COPD Exacerbations: Exacerbations of emphysema or chronic obstructive pulmonary disorder (COPD) have been reported with a risk of up to 11 percent²⁹ in one small case series of 9 patients who had non-calypso beacons implanted. However, several much larger case series reported no COPD exacerbations^{24,27,28} whatsoever.

Beacon Migration: Beacon migration has been reported at a rate of 1%²⁴ using anchored calypso beacons which can lead to the expectoration of the migrated beacon.

Infection: There is a 1% risk of pulmonary infection in the tissue in close proximity to an anchored Calypso beacon²⁴.

Minor Bleeding: There is a small risk of minor local bleeding in the airway implanted with the transponder beacon with a risk similar to other bronchoscopic based procedures, however no pulmonary hemorrhages were reported in the case series using the anchored Calypso lung beacon²⁴.

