MRI compatibility: Anchored Calypso beacons can be safely scanned using MRI with either a 1.5 or 3.0 Tesla static magnetic field with or a magnetic field gradient of up to 9.3 Tesla/meter without inducing any clinically significant displacement force or torque. An MRI image artifact may extend up to 2 cm from the anchored transponder, which is of no clinical significance for patients on this trial since, outside of research studies, MRI is not used in the routine diagnosis of intrapulmonary lesions.

Retrieval of Calypso Beacons:

If an unanticipated adverse effect occurs with a Calypso beacon and removal of the beacon is required, then the anchored beacons can be retrieved using a flexible bronchoscope and forceps similar to other endobronchial foreign body retrievals.

12. 0 Evaluation During and After Protocol Treatment

| | Baseline | 4DCT Sim* | Each SABR Fraction[¶] | 2 mo[#] | 6 mo | 12 mo | 18 mo | 2 yr | 3 yr |
|------------------------------------|------------------------|-----------------------------|--|------------------------------------|------------------------|-------------------------|-------------------------|--------------------|--------------------|
| History & Physical Exam | x | | | x | x | x | x | x | x |
| CT or MRI Brain | x | | | | | | | | |
| CT Chest & Abdomen | x | | | | x | x | x | x | x |
| PET Scan | x | | | | | | | | |
| Chest X-ray | | | | x | | | | | |
| Pulmonary | x | | | | x | | x | | x |

| Function Testing | | | | | | | | | |
|--------------------------------|---|---|---|---|---|---|---|---|---|
| 6 min walking test | x | | | | x | | x | | x |
| Medication Profile | x | | | x | x | x | x | x | x |
| CBC, Lytes, Bun, Cr | x | | | | | | | | |
| EORTC QLQ - LC13 | x | x | x | x | x | x | x | x | x |
| Toxicity Profile (CTCAE V 4.0) | x | x | x | x | x | x | x | x | x |
| Inter-beacon distance | | x | x | | | | | | |

Notes:

* 4DCT is to be performed no later than 4 calendar weeks after the date of beacon implantation

φ The first fraction of SABR is to start no later than 14 calendar days after the 4DCT simulation scan

the timing of all follow up evaluations are relative to the date of the last fraction of SABR.

13.0 Statistical Considerations:Descriptive characteristics:

Baseline patient, tumor, and treatment characteristics will be summarized using standard descriptive statistics as summarized in the table below.

| Patient Factors | |

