APPENDIX I – EORTC QLQ - LC13 Quality of Life Questionnaire (Lung Cancer)

**EORTC QLQ - LC13**

Patients sometimes report that they have the following symptoms or problems. Please indicate the extent to which you have experienced these symptoms or problems during the past week. Please answer by circling the number that best applies to you.

| During the past week : | Not at All | A Little | Quite a Bit | Very Much |
|---|-----------------------|---------------------|------------------------|----------------------|
| 31. How much did you cough? | 1 | 2 | 3 | 4 |
| 32. Did you cough up blood? | 1 | 2 | 3 | 4 |
| 33. Were you short of breath when you rested? | 1 | 2 | 3 | 4 |
| 34. Were you short of breath when you walked? | 1 | 2 | 3 | 4 |
| 35. Were you short of breath when you climbed stairs? | 1 | 2 | 3 | 4 |
| 36. Have you had a sore mouth or tongue? | 1 | 2 | 3 | 4 |
| 37. Have you had trouble swallowing? | 1 | 2 | 3 | 4 |
| 38. Have you had tingling hands or feet? | 1 | 2 | 3 | 4 |
| 39. Have you had hair loss? | 1 | 2 | 3 | 4 |
| 40. Have you had pain in your chest? | 1 | 2 | 3 | 4 |
| 41. Have you had pain in your arm or shoulder? | 1 | 2 | 3 | 4 |
| 42. Have you had pain in other parts of your body? | 1 | 2 | 3 | 4 |
| If yes, where _____ | | | | |
| 43. Did you take any medicine for pain? | | | | |
| 1 No 2 Yes | | | | |
| If yes, how much did it help? | 1 | 2 | 3 | 4 |

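### No toxicity assessment is scheduled between baseline and 4DCT, up to 4 weeks after beacon implantation, so non-serious transient implantation events may be under-recorded

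*Combined protocol and SAP*

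**What the plan says.** Section 6.0 lists, as phase I objective 4, "To assess acute toxicity of beacon implantation using the Common Terminology for Criteria for Adverse Events (CTCAE version 4.0"). The phase I hypothesis in the same section is that placement will prove safe and tolerable. Section 7.0 makes acute and late CTCAE toxicity a secondary endpoint without tying it to a phase. Under Section 1.0, patients in both phases (2 and 26) have beacons placed.

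The Section 12.0 table schedules CTCAE and QLQ-LC13 at baseline, at 4DCT simulation, at each SABR fraction, and then at 2, 6, 12 and 18 months and 2 and 3 years. It has no column for the implantation day or the days after it. The notes to the table fix the timing. On the simulation scan they say: "4DCT is to be performed no later than 4 calendar weeks after the date of beacon implantation". Treatment must then begin within two weeks of that scan. On the visits after treatment they add that "the timing of all follow up evaluations are relative to the date of the last fraction of SABR".

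Section 11.0 names pneumothorax as the commonest complication of marker placement, with a risk of 2 to 5 percent, "with the majority of these treated either conservatively or with a pigtail catheter for a day or two" afterwards. Section 13.0 tabulates the maximum toxicity grade seen over treatment and follow-up. It gives no start date, recall period or denominator.

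**The concern.** The schedule leaves the period in which implantation complications are most likely without a planned assessment. An event that needs only observation, or a catheter for a day or two, can be over well before the first post-implant CTCAE visit. Nothing tells the assessor at that visit to ask back to the procedure. The questionnaire does not fill the gap, because it asks patients to "Please indicate the extent to which you have experienced these symptoms or problems during the past week".

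The second weakness is the anchor. Follow-up dates are undefined for a patient who has no SABR fraction. If such patients drop out of the toxicity table, the loss can be selective, because a complication of placement is one possible reason for not going on to SABR.

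At stake is the description of implantation toxicity. Section 1.0 intends the toxicity data to help design a phase III trial, in which placement would be an added risk of the Calypso approach. Events missed in this way can only lower the reported rate.

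**Working it through.** The protocol states no figure for implantation toxicity in this trial, so there is none to reproduce. Its one design figure, power 0.92 (Section 13.0), does reproduce with a one-sample normal approximation: difference 0.4 × 62.9 = 25.16 cm³; standard error 43.6/√28 = 8.24; Φ(25.16/8.24 − 1.645) = 0.92. It does not depend on the toxicity schedule.

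**Step 1: the gap (Section 12.0 notes).** Implantation to first scheduled CTCAE: at most 4 × 7 = 28 days. Implantation to first fraction: at most 28 + 14 = 42 days. Both are upper limits, not expected intervals.

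**Step 2: which patients have which assessments.**
- Implanted, simulated and treated: first post-implant CTCAE at 4DCT, then the full schedule.
- Implanted and simulated, no SABR: the 4DCT assessment only.
- Implanted, never simulated: no scheduled post-implant assessment. Section 16.0 leaves further follow-up to recommendation by the principal investigators.

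**Step 3: what SAE reporting covers.** In Appendix II, pneumothorax is grade 1 if asymptomatic and grade 2 if symptomatic with intervention such as a tube; hospitalization first appears at grade 3. Section 17.0 counts admission as serious, and also important medical events without admission, on medical judgment. The remaining exposure is grade 1-2 events not judged serious.

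**Step 4: expected events.** Expected number = n × p; chance of at least one = 1 − (1 − p)^n.

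| Event and risk (Section 11.0) | n | Expected | Chance of ≥ 1 |
|---|---|---|---|
| Pneumothorax, 2% | 28 | 0.56 | 1 − 0.98^28 = 43% |
| Pneumothorax, 5% | 28 | 1.40 | 1 − 0.95^28 = 76% |
| Pneumothorax, 2% | 2 | 0.04 | 1 − 0.98² = 4% |
| Pneumothorax, 5% | 2 | 0.10 | 1 − 0.95² = 10% |
| COPD exacerbation, 0% to 11% | 28 | 0 to 3.1 | 0% to 96% |

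The 11% comes from a series of 9 patients with non-Calypso markers. Section 11.0 adds that several much larger series saw none, so 3.1 is a ceiling.

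**Step 5: effect of incomplete recording (assumption).** The protocol gives no capture rate. For pneumothorax in 28 patients, with a share c recorded, expected = 28 × p × c:
- c = 75%: 0.42 to 1.05 recorded; chance of recording at least one 35% to 66%.
- c = 50%: 0.28 to 0.70; 25% to 51%.
- c = 25%: 0.14 to 0.35; 13% to 30%.

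**Step 6: effect of the denominator (assumption).** Suppose one of 28 implanted patients has a complication, never reaches SABR and is left out. The result moves from 1/28 = 3.6% (one-sided 95% upper bound 15.9%) to 0/27 (upper bound 1 − 0.05^(1/27) = 10.5%).

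**The case against.** The strongest reply is that the protocol has more safety capture than the table shows. SAE reporting (Section 17.0) applies regardless of cause, is due within 24 hours of knowledge, and depends neither on visits nor on SABR. A tube-drained pneumothorax could qualify without admission. The 4DCT CTCAE falls after implantation and before SABR, and nothing confines it to what is present that day. Section 10.0 places beacon placement under treatment, which favours counting its events in the Section 13.0 table. All of this stands, and it limits the point to non-serious events and the denominator.

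Several stronger readings are tempting but not supported:

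- A reader might infer that implantation events will be under-counted. The documents show only a risk, because the 4DCT assessment may pick up earlier events.
- A reader might apply the 43% to 76% figure to the phase I safety hypothesis. That hypothesis and objective 4 concern two patients. Even with perfect recording, zero events in two leaves a one-sided 95% upper bound of 1 − 0.05^(1/2) = 77.6%. The 28-patient figures belong to the general toxicity endpoint.
- A reader might infer from Section 5.0, where upper-lobe motion is judged "as assessed by fluoroscopy at the time of bronchoscopy", that patients found ineligible will already carry beacons. The text does not say that this is the implantation bronchoscopy, and Section 9.0 requires eligibility to be confirmed before enrollment.
- A reader might treat placement as the investigational step of phase II. Section 2.0 says the beacon was already approved for routine implantation; phase II evaluates gated SABR with reduced margins.
- A reader might take the questionnaire to miss the procedure in every patient. That depends on when the scan falls: at the 28-day limit it covers days 21 to 28, but a scan within a week of placement would include the procedure.

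**Conclusion.** The point holds in a limited form. The schedule has no CTCAE assessment between baseline and 4DCT, sets no look-back, and gives an implanted but never simulated patient no scheduled assessment. Non-serious, transient implantation events may therefore be under-recorded, and any resulting bias is downward. Serious events remain covered.

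The numbers are small, which is why single events matter: about one pneumothorax is expected across 28 implantations (0.56 to 1.4), so one missed event can turn a recorded complication into none. In the two phase I patients the chance of any pneumothorax is only 4% to 10%. This rests on all 28 patients being implanted and on the Section 11.0 risks applying here. How many events would be missed, and how many patients would not reach SABR, cannot be derived from the documents.

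The change is worth making. It does not bear on the primary endpoints or the sample size.

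**What to change.** 1. Add a beacon-placement column to the Section 12.0 table, with a CTCAE assessment on the procedure day and one telephone CTCAE contact within about 7 days, made by existing staff.
2. State in the notes that the 4DCT CTCAE records the worst grade since implantation.
3. State in Section 13.0 that implantation toxicity is reported on all patients in whom placement was attempted, including those who do not go on to simulation or SABR.
4. For patients who do not reach SABR, date the toxicity assessments from the procedure.

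The 7-day interval is a practical choice; another early contact would serve if it is fixed in advance.

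The cost is one extra column and one telephone contact per patient, 28 in all, with no added imaging or procedure. The reported complication rate may come out slightly higher. The PTV endpoint and the power calculation do not change.

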- 5) To quantify the potential benefit of continuous monitoring of tumor location using Calypso by comparing it to traditional imaging-based setup.

Phase II:

- 1) To quantitatively assess the differences in irradiated treatment volumes and radiotherapy dose volume metrics for the PTV and healthy thoracic organs at risk between Calypso™ guided respiratory gated SABR and the traditional ITV based radiotherapy.
- 2) To serially quantify the acute and late toxicity of patients undergoing Calypso™ guided SABR using the Common Terminology Criteria for Adverse Events (CTCAE) Version 4.0
- 3) To serially quantify the self-reported quality of life of patients undergoing Calypso Guided SABR using the EORTC QLQ - LC13 questionnaire
- 4) To serially biobank blood and urine samples for patients undergoing radical SABR of lung tumors to allow for the future development of novel prognostic and predictive biomarkers for patients undergoing SABR.
- 5) To serially quantify changes to pulmonary function following SABR treatment

- 6) To demonstrate the benefit of Calypso treatments in reducing patient-specific component of PTV margins

Study Hypotheses:

Phase I: Calypso beacon placement will be safe and well tolerated and will function within their specified tolerances with minimal (sub-millimeter) inter-beacon migration.

Phase II: The Median Planning Target Volume (PTV) of Calypso guided respiratory gated SABR will be 40% smaller than the median PTV volume of standard ITV based SABR treatment with standard PTV margins. Furthermore, thoracic organs at risk will receive significantly less radiotherapy dose when compared to the standard SABR treatment.

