- 6) Kidneys (if the tumor is a lower lobe tumor);
- 7) Ipsilateral brachial plexus (if located within 5 cm of the PTV);
- 8) Spinal Cord;
- 9) Proximal Trachea;
- 10) Proximal bronchial tree;
- 11) Aorta (if left sided tumor);
- 12) Vena Cava (if right sided tumor);
- 13) Liver (if tumor is located in the right lower lobe)
- 14) Nearest vertebral body, and the vertebral body above and below the nearest vertebral body.

For organ at risk contouring guidelines, radiation oncologists are encouraged to reference the RTOG 0236 trial protocol.

Target Volume Delineation:

The Gross Tumor Volume (GTV) will be delineated on all 10 respiratory-phase correlated CT datasets with the CT Hounsfield unit window level set to the “lung window” preset. Participating radiation oncologists are encouraged to cross-reference the pre-treatment investigations (Infused CT chest, PET scan, etc) in order to aid with the delineation of the GTV.

Internal Target Volume: Using the average CT dataset, the ITV will be generated using the Eclipse™ “accumulate structure” function incorporating the GTVs created on all 10 phase-correlated datasets.

Gating Window Internal Target Volume (ITV_{GW}): The ITV_{GW} will consist of a accumulated structure composed of the GTVs contoured on the end-exhalation phases of the breathing cycle. The end-exhalation phases will typically include the GTVs from the CT50, CT40, and CT60 phases of the 4DCT scan. Depending on the individual patient’s breathing pattern, the ITV_{GW} could also include the GTVs from CT30 and CT70 if necessary (this decision to include CT30 and CT70 needs to be approved by the study PI on a case-by-case basis).

Planning Target Volume expansion margins:

For Phase I of the study - 5 mm isotropic expansion of the ITV

For Phase II of the study - 3mm isotropic expansion of the ITV_{GW}.

Note: For patients treated in phase II of the study, If setup errors noted during the first fraction of treatment are greater than 3mm in size for more than 10% of the overall treatment time, then a larger, case-specific PTV margin will be applied for the remaining 2 fractions of the radiotherapy. Any enlargements to the PTV will be applied with the prior approval of the study PI.

Radiotherapy Dose Prescription: 54 Gy to 95% of PTV in 3 fractions.

Radiotherapy Dose Coverage: 99% of the PTV receives at least 90% of prescription dose

Timing of Fractions: A minimum of 40 hours should separate each fraction.

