|--|---------------------------|
| Age | Mean & Standard Deviation |
| Gender | Percentage |
| Comorbidity (Charlson Index) | Mean & Standard Deviation |
| Smoking History Category (Current smoker, previous smoker, never smoker) | Percentage |
| Smoking Pack-Year History | Mean & Standard Deviation |
| FEV1 (Liters) | Mean & Standard Deviation |
| Diffusion Capacity (%) | Mean & Standard Deviation |
| 6 Minute Walk Test (% of expected distance) | Mean & Standard Deviation |
| Tumor Factors | |
| T-stage (T1, T2) | Percentage |
| Tumor size (cm ³) | Mean & Standard Deviation |
| Tumor location (by lobe) | Percentage |
| Tumor Histology | Percentage |
| Treatment Factors | |
| GTV (cm ³) | Mean & Standard Deviation |
| PTV (cm ³) | Mean & Standard Deviation |
| Maximal observer tumor motion (cm) | Mean & Standard Deviation |
| Radiotherapy Dose Prescription (cGy) | Percentage |
| Radiotherapy Delivery Time Per Fraction | Mean & Standard Deviation |

Study Power:

Power calculations were conducted using the STATA 12.0 statistical software package (College station, Texas). Zhao *et al.*²² carried out dosimetric analyses of lung tumors undergoing SABR lung treatments with similar characteristics (T1-T2N0 NSCLC) to those which would be eligible for this study and found a median PTV volume of 62.9 cm³ (sd 43.6 cm³). Presuming similar sized tumor volumes as Zhao *et al.*, A sample size of 28 patients would yield a power of 0.92 to detect a 40% reduction in the mean PTV volume between standard ITV based SABR treatment as compared to gated calypso guided SABR, with an alpha value of 0.05 and using a 1-sided test for statistical significance.

Endpoints:

Percentage Change in PTV: For each participating patient, the PTV volumes will be calculated on the same 4DCT for standard ITV-based SABR treatment as well as the Calypso guided SABR treatment. The comparison of the PTV volumes will be calculated as follows:

$$\% \text{ change in PTV} = (\text{PTV}_{\text{standard SABR}} - \text{PTV}_{\text{Calypso Guided SABR}}) / (\text{PTV}_{\text{standard SABR}}) \times 100$$

This metric will be reported as a mean for the cohort with SD

Quality of Life Data: The mean EORTC QLQ – LC13 plus standard deviation will be tabulated in descriptive format for each evaluation time point.

Acute and Late Toxicity: The maximum grade of observed toxicity during treatment and follow-up will be tabulated in a descriptive format by adverse effect.

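### The Phase II power figure matches only a test against zero PTV reduction, which the planning geometry already excludes, and the plan sets no criterion for its 40% hypothesis

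*Combined protocol and SAP*

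**What the plan says.** Section 6.0 (Study Hypotheses) predicts that the median PTV of gated SABR "will be 40% smaller than the median PTV volume of standard ITV based SABR treatment". Section 7.0 makes the mean within-patient percentage difference in PTV the Phase II primary endpoint.

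Section 13.0 (Study Power) takes a PTV of 62.9 cm³ with SD 43.6 cm³ from a published dosimetric study and states: "A sample size of 28 patients would yield a power of 0.92 to detect a 40% reduction in the mean PTV volume", "with an alpha value of 0.05 and using a 1-sided test for statistical significance". Under Endpoints, both PTVs are computed for each patient on one 4DCT, and the analysis is given as: "This metric will be reported as a mean for the cohort with SD". No null value, named test, confidence interval or success rule appears.

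Section 10.0 (Target Volume Delineation) forms the standard ITV from the GTVs on all ten respiratory phases. For gating, "The ITV_{GW} will consist of a accumulated structure composed of the GTVs contoured on the end-exhalation phases of the breathing cycle": three phases as a rule, up to five with approval. The margin is 5 mm on the ITV in Phase I and 3 mm on ITV_GW in Phase II, whereas the Section 1.0 schema gives 2 mm for Phase II. If fraction 1 shows setup errors above 3 mm for more than 10% of treatment time, "then a larger, case-specific PTV margin will be applied for the remaining 2 fractions of the radiotherapy".

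**The concern.** A test is informative only if its null could be true. Here the planned gated PTV is smaller than the standard one by definition, before any patient is scanned. Rejecting zero would confirm the definitions and say nothing about whether tracking or gating achieved something worthwhile.

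The quantity the investigators care about, 40%, enters only as the alternative in the power calculation. Without a stated rule, a mean reduction well short of 40% could be reported as a statistically significant confirmation.

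The reduction also combines two sources: the margin that the protocol chose to shrink, and the motion removed by gating. Section 2.0 says tumours moving less than 1 cm do not seem to benefit meaningfully from gating, yet Section 5.0 requires 1 cm of motion only for upper-lobe tumours. A nearly static lower-lobe tumour can therefore enrol and still show a sizeable reduction.

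Finally, a patient whose small margin proves inadequate at fraction 1 may still enter the endpoint with that small margin, because the formula does not say which PTV is used.

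**Working it through.** **1. Reproducing the stated power.** Inputs from Section 13.0: PTV 62.9 cm³, SD 43.6 cm³, 40% reduction, one-sided alpha 0.05, n = 28.

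- Difference: 0.40 × 62.9 = 25.16 cm³.
- Standard error: 43.6/√28 = 8.24 cm³.
- One-sample normal power against zero: Φ(25.16/8.24 − 1.645) = Φ(1.409) = 0.9205, the stated 0.92.
- With the 26 Phase II patients: 43.6/√26 = 8.55; Φ(25.16/8.55 − 1.645) = 0.903.

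Other nulls, same inputs, true reduction 40%: power is 0.74 for a 10% null, 0.45 for 20%, 0.19 for 30% and 0.05 for 40%. A two-sided one-sample test gives 0.863, and a one-sided two-sample test with 28 per arm gives 0.697. The t version of the one-sample test against zero gives 0.908. Only a one-sided one-sample test against zero fits.

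**2. Why zero is excluded for planned volumes.** ITV_GW is the union of 3 to 5 of the 10 GTVs whose union is the ITV, so ITV_GW lies inside the ITV. Expanding the inner volume by 3 mm (or 2 mm) and the outer by 5 mm keeps the first strictly inside the second. This holds for every patient and for either Phase II margin. The 5 mm margin is stated for Phase I and is taken here as the Phase II comparator.

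**3. How much the margin alone contributes.** For a static sphere of radius r mm, with no motion and hence no gating effect, reduction = 1 − ((r + m)/(r + 5))³.

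| Diameter | m = 3 mm | m = 2 mm |
|---|---|---|
| 4 cm (r = 20) | 1 − (23/25)³ = 22.1% | 1 − (22/25)³ = 31.9% |
| 2.5 cm (r = 12.5) | 1 − (15.5/17.5)³ = 30.5% | 1 − (14.5/17.5)³ = 43.1% |
| 2 cm (r = 10) | 1 − (13/15)³ = 34.9% | 1 − (12/15)³ = 48.8% |

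The conflict between 2 mm and 3 mm changes the built-in reduction by about 10 to 14 points.

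**4. Illustration on assumed inputs.** Simulated trials (20,000) used n = 26, a 3 mm margin, GTV radius 7.5 to 19.9 mm, motion 0 to 5 mm and residual gated motion of 20%. None of these distributions is in the documents. The mean reduction was 34.6%. A test against zero rejected in 100% of trials; a test against 40% rejected in none.

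**5. Enlarged margins, also illustrative.** Take an assumed cohort with 45.2% reduction as planned and 20.7% for ITV_GW + 5 mm. A patient enlarged to 5 mm for two of three fractions averages 45.2/3 + 2 × 20.7/3 = 28.9%. If 20% of patients are enlarged, the cohort mean is 0.8 × 45.2 + 0.2 × 28.9 = 41.9%; if 30%, 40.3%. The enlargement rates and the 5 mm size are assumptions; Section 10.0 states neither.

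**The case against.** The plan can be read as estimation. The Phase II objective is to assess differences quantitatively, the written analysis is a mean with SD, and the zero null is inferred from the power figure. That is fair. It does not rescue the power statement, which justifies the sample size by a significance test, and it leaves 40% without a criterion.

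The endpoint is deliberately a package: gating together with Calypso-based margins. That also stands, so the split of margin from gating is supportive and the primary endpoint need not change.

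Some stronger readings are tempting but not supported:

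- *The trial cannot fail.* This is exact only for planned volumes. The enlargement has no stated cap, and enlarged PTVs might enter the endpoint. In simulation with motion up to 5 mm, enlarging to 7 mm in 25% or 50% of patients cut rejection of zero to 94% or 14%.
- *Success could be declared at about 22%.* One can compute 1.645 × 43.6/√28 = 13.55 cm³, or 21.5% of 62.9. But 43.6 is a between-patient SD of volume and the endpoint is a within-patient percentage. With an assumed within-patient SD of 10 to 20 points, a one-sided test at n = 26 would reject above about 3.4% to 6.7%. No document sets a success bar at all.
- *The data could not show whether 40% was met.* A mean, SD and n yield a confidence interval. What is missing is a rule fixed in advance.
- *Small-margin failures will inflate the result.* The plan is silent on which PTV counts, so this is possible but not established.

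**Conclusion.** The concern holds in this form. The Phase II power figure corresponds to a one-sided test against zero reduction (0.9205 at n = 28, 0.903 at n = 26). For the planned volumes, the protocol's own target definitions exclude that null. No null, interval or criterion addresses the 40% hypothesis. The margin change alone supplies about 22% to 35% (5 to 3 mm) or 32% to 49% (5 to 2 mm), so a significant reduction would not be specific to gating. The PTV to be used after a fraction-1 enlargement is undefined.

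The exclusion of zero needs only set inclusion and the 5 mm comparator. The margin-only percentages assume static spheres of 4 to 2 cm. The simulation and enlargement figures are illustrations and the conclusion does not depend on them.

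**What to change.** (a) Report the mean within-patient percentage reduction with a two-sided 95% confidence interval, and base the conclusion on where that interval lies relative to 40% (wholly above, containing, or wholly below), not on a test against zero. Replace the power statement with precision for n = 26. The half-width is 2.06 × SD/√26, about 4.0, 6.1 or 8.1 points for an SD of 10, 15 or 20 points. That SD range is assumed, since the documents give none. Requiring the interval to clear 40% would be demanding: even a one-sided 0.05 test against 40% needs a true mean of about 44.9% to 49.8% for 80% power over that SD range.

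(b) From the same contours, also compute ITV plus the Phase II margin and ITV_GW plus 5 mm, and report them as a supportive split of margin from gating.

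(c) State which PTV is primary, and also report the fraction-weighted PTV actually used in patients whose margin was enlarged.

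(d) Reconcile the 2 mm and 3 mm passages, and state the comparator margin for Phase II.

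The cost is revised Section 13.0 wording and two automated expansions per patient. Treatment is not affected. The reported benefit may look smaller.
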